8.3 ADVERSE EVENTS (AES), SERIOUS ADVERSE EVENTS (SAES) AND OTHER SAFETY REPORTING

The definitions of adverse events (AEs) and serious adverse events (SAEs) can be found in Appendix 3 ([Section 10.3](#)). The definition of adverse event of special interest (AESI) is provided in [Section 8.3.8](#).

AE will be reported by the participant (or, when appropriate, by a caregiver, surrogate, or the participant's legally authorized representative).

The Investigator and any qualified designees are responsible for detecting, documenting, and recording events that meet the definition of an AE or SAE and remain responsible for following up AEs that are serious, considered related to the study intervention or study procedures, or that caused the participant to discontinue the study intervention (see [Section 7](#)).

The method of recording, evaluating, and assessing causality of AEs and SAEs and the procedures for completing and transmitting SAE reports are provided in Appendix 3 ([Section 10.3](#)).

8.3.1 Time period and frequency for collecting AE and SAE information

All AEs, including adverse events of new onset, as well as worsening of baseline signs and symptoms will be collected throughout study period, from the signing of the informed consent form (ICF) until **30 days** following cessation of study treatment.

All SAEs and AESIs will be collected throughout the study period, from the signing of the informed consent form (ICF) until **3 months** following last administration of study treatment.

All SAEs and AESI will be recorded and reported to the Sponsor or designee immediately and under no circumstance should this exceed 24 hours, as indicated in Appendix 3 ([Section 10.3](#)). The Investigator will submit any updated SAE data to the Sponsor within 24 hours of it being available.

Investigators are not obligated to actively seek information on AEs or SAEs after conclusion of the study participation. However, if the Investigator learns of any SAE, including a death, at any time after a participant has been discharged from the study, and he/she considers the event to be reasonably related to the study intervention or study participation, the Investigator must promptly notify the Sponsor.

8.3.2 Method of detecting AEs and SAEs

Care will be taken not to introduce bias when detecting AEs and/or SAEs. Open-ended and non-leading verbal questioning of the participant is the preferred method to inquire about AE occurrences.

8.3.3 Follow-up of AEs and SAEs

After the initial AE/AESI/SAE report, the Investigator is required to proactively follow each participant at subsequent visits/contacts. At the pre-specified study end-date, all SAEs, and AESIs (as defined in [Section 8.3.8](#)), will be followed until resolution, stabilization, the event is otherwise explained, or the participant is lost to follow-up (as defined in [Section 7.3](#)). Stabilization is defined as an AE ongoing without any change for at least 3 months. Participants with an AE of Grade >1 will be further followed until the resolution of the AE to Grade 0-1 or starting of a new antineoplastic therapy, whichever occurs first.

Further information on follow-up procedures is provided in Appendix 3 ([Section 10.3](#)).

8.3.4 Regulatory reporting requirements for SAEs

- Prompt notification by the Investigator to the Sponsor of an SAE is essential so that legal obligations and ethical responsibilities towards the safety of participants and the safety of a study intervention under clinical investigation are met.
- The Sponsor has a legal responsibility to notify both the local regulatory authority and other regulatory agencies about the safety of a study intervention under clinical investigation. The Sponsor will comply with country-specific regulatory requirements

relating to safety reporting to the regulatory authority, Institutional Review Boards (IRB)/Independent Ethics Committees (IEC), and Investigators.

- Serious adverse events (SAEs) that are considered expected will be specified in the reference safety information (IB for SAR444245).
- Investigator safety reports must be prepared for suspected unexpected serious adverse reactions (SUSARs) according to local regulatory requirements and Sponsor policy and forwarded to Investigators as necessary.
- An Investigator who receives an Investigator safety report describing an SAE, SUSAR or any other specific safety information (eg, summary or listing of SAEs) from the Sponsor will review and then file it along with the IB and will notify the IRB/IEC, if appropriate according to local requirements. It is the responsibility of the Sponsor to assess whether an event meets the criteria for a SUSAR, and therefore, should be expedited to regulatory authorities.

8.3.5 Pregnancy

- Details of all pregnancies in female participants and female partners of male participants will be collected after the start of study intervention and until 120 days (or refer to the individual substudy protocol) following cessation of study treatment, or 30 days following cessation of study treatment if the participant initiates another anticancer therapy
- If a pregnancy is reported, the Investigator will record pregnancy information on the appropriate form and submit it to the Sponsor within 24 hours of learning of the female participant or female partner of male participant (after obtaining the necessary signed informed consent from the female partner) pregnancy.
- Abnormal pregnancy outcomes (eg, spontaneous abortion, fetal death, stillbirth, congenital anomalies, ectopic pregnancy) are considered SAEs and will be reported as such.
- The participant /pregnant female partner will be followed to determine the outcome of the pregnancy. The Investigator will collect follow-up information on the participant /pregnant female partner and the neonate, and the information will be forwarded to the Sponsor.
- Any post-study pregnancy-related SAE considered reasonably related to the study intervention by the Investigator will be reported to the Sponsor as described in [Section 8.3.4](#). While the Investigator is not obligated to actively seek this information in former study participants /pregnant female partner, he or she may learn of an SAE through spontaneous reporting.
- Any female participant who becomes pregnant while participating in the study will discontinue study intervention.

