safety (as per Schedule of Activities [SoA] in the individual substudy) and tumor imaging assessments, until PD, start of another anticancer therapy, final cohort cut-off, whichever comes first, before moving to the Survival Phone Call Follow-Up Period.

2. Participants who discontinue study treatment **with PD** (per Lugano response criteria 2014[2]) will be followed for safety in the Follow-Up Visit 1 occurring 3 months ± 7 days from last IMP administration, before moving to the Survival Phone Call Follow-Up Period.

Participants who move into the **Survival Phone Call Follow-up Period** will be contacted by telephone every 3 months ± 14 days to assess for survival status. Updated survival status may be requested by the Sponsor at any time during the study. Survival Phone Call Follow up will continue until death, participant request to discontinue from follow-up, or cut-off date for final analysis has been reached, or upon cancellation of Survival follow-up at the discretion of the Sponsor at any prior timepoint.

After the cohort cut-off date for the primary analysis, participants can continue to receive IMP, if clinical benefit is observed, until full permanent discontinuation criteria described in [Section 7](#) are met and will continue to undergo all assessments as per the study schedule of activities in the individual substudy.

For each cohort, the cut-off date for the final analysis (ie, analysis of secondary objectives and update of the primary objective) will be 3 years from cohort last participant in (LPI).

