a) Male participants

Male participants are eligible to participate if they agree to the following during the intervention period and for at least 3 days [corresponding to time needed to eliminate SAR444245] after the last dose of SAR444245:

- Refrain from donating or cryopreserving sperm.

PLUS either:

- Be abstinent from heterosexual intercourse as their preferred and usual lifestyle (abstinent on a long term and persistent basis) and agree to remain abstinent.

OR

- Must agree to use contraception/barrier as detailed below
- A male condom when having sexual intercourse with a woman of childbearing potential (WOCBP) who is not currently pregnant, or during homosexual intercourse. The participant should also be advised of the benefit for a female partner to use a highly effective method of contraception (as described in Appendix 4 Contraceptive and barrier requirements [[Section 10.4](#)]) as a condom may break or leak when having sexual intercourse with a woman of childbearing potential (WOCBP) who is not currently pregnant.

b) Female participants

A female participant is eligible to participate if she is not pregnant or breastfeeding, and at least one of the following conditions applies:

- Is not a woman of childbearing potential (WOCBP).

OR

- Is a WOCBP and agrees to use a contraceptive method that is highly effective (with a failure rate of $<1\%$ per year), with low user dependency, as described in Appendix 4 ([Section 10.4](#)) during the intervention period (to be effective before starting the

intervention) and for at least 120 days (or refer to the individual substudy protocol [corresponding to the time needed to eliminate any study intervention(s)] after the last dose of study intervention and agrees not to donate or cryopreserve eggs (ova, oocytes) for the purpose of reproduction during this period.

- A WOCBP must have a negative highly sensitive pregnancy test (as required by local regulations) within 72 hours before the first dose of study intervention.
- Additional requirements for pregnancy testing during and after study intervention are located in Appendix 4 ([Section 10.4](#)).
- The Investigator is responsible for review of medical history, menstrual history, and recent sexual activity to decrease the risk for inclusion of a woman with an early undetected pregnancy.

Informed Consent

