8.2.5 Pregnancy testing

- Refer to [Section 5.1](#) Inclusion criteria 05 for pregnancy testing criteria; the Investigator is responsible for review of medical history, menstrual history, and recent sexual activity to decrease the risk for inclusion of a woman with an early undetected pregnancy
- Women of childbearing potential must have a negative urine pregnancy test result within 72 hours prior to first IMP administration of each cycle, at EOT and every 30 (± 7) days until 120 days (or refer to the individual substudy protocol) after the last dose of study treatment. If urine pregnancy results cannot be confirmed as negative, a serum pregnancy test will be required. Pregnancy tests (serum and/or urine tests) should be repeated if required by local guidelines.

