8.3.8 Adverse event of special interest

Adverse event of special interest

An AESI is an AE (serious or nonserious) of scientific and medical concern specific to the Sponsor's product or program, for which ongoing monitoring and immediate notification by the Investigator to the Sponsor is required. Such events may require further investigation in order to characterize and understand them. Adverse events of special interest may be added, modified or removed during a study by protocol amendment. The following events need to be reported as AESIs:

- Pregnancy of a female participant entered in a study as well as pregnancy occurring in a female partner of a male participant entered in a study with IMP/NIMP
 - Pregnancy occurring in a female participant entered in the clinical trial or in a female partner of a male participant entered in the clinical trial. It will be qualified as an SAE only if it fulfills one of the seriousness criteria (see Appendix 3 [[Section 10.3](#)]).
 - In the event of pregnancy in a female participant, IMP should be discontinued.
 - Follow-up of the pregnancy in a female participant or in a female partner of a male participant is mandatory until the outcome has been determined (See Appendix 4 [[Section 10.4](#)]).
- Symptomatic overdose (serious or nonserious) with IMP/NIMP
 - An overdose of IMP is defined as: increase of at least 30% of the dose to be administered in the specified duration or if the dose is administered in less than half the recommended duration of administration.
 - An overdose (accidental or intentional) with the NIMP is an event suspected by the Investigator or spontaneously notified by the participant (not based on systematic pills count) and defined as at least twice the intended dose within the intended therapeutic interval, adjusted according to the tested drug.
- An elevated AST or ALT lab value that is greater than or equal to 3X the ULN and an elevated total bilirubin lab value that is greater than or equal to 2X the ULN and, at the same time, an alkaline phosphatase lab value that is less than 2X the ULN, as determined by way of protocol-specified laboratory testing or unscheduled laboratory testing*.

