Note: Periodic abstinence (calendar, symptothermal, post-ovulation methods), withdrawal (coitus interruptus), spermicides only, and lactational amenorrhoea method (LAM) are not acceptable methods of contraception. Male condom and female condom should not be used together (due to risk of failure with friction).

[figure not shown]
COLLECTION OF PREGNANCY INFORMATION:**Male participants with partners who become pregnant**

- The Investigator will attempt to collect pregnancy information on any male participant's female partner who becomes pregnant while the male participant is in this study. This applies only to male participants who receive study intervention.
- After obtaining the necessary signed informed consent from the pregnant female partner directly, the Investigator will record pregnancy information on the appropriate form and submit it to the Sponsor within 24 hours of learning of the partner's pregnancy. The female partner will also be followed to determine the outcome of the pregnancy. Information on the status of the mother and child will be forwarded to the Sponsor. Generally, the follow-up will be no longer than 6 to 8 weeks following the estimated delivery date. Any termination of the pregnancy will be reported regardless of fetal status (presence or absence of anomalies) or indication for the procedure.

Female participants who become pregnant

- The Investigator will collect pregnancy information on any female participant who becomes pregnant while participating in this study. The initial information will be recorded on the appropriate form and submitted to the Sponsor within 24 hours of learning of a participant's pregnancy.
- The participant will be followed to determine the outcome of the pregnancy. The Investigator will collect follow-up information on the participant and the neonate and the information will be forwarded to the Sponsor. Generally, follow-up will not be required for longer than 6 to 8 weeks beyond the estimated delivery date. Any termination of pregnancy will be reported, regardless of fetal status (presence or absence of anomalies) or indication for the procedure.
- Any pregnancy complication or elective termination of a pregnancy for medical reasons will be reported as an AE or SAE.
- A spontaneous abortion (occurring at <22 weeks gestational age) or still birth (occurring at >22 weeks gestational age) is always considered to be an SAE and will be reported as such.

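### Section 8.3.5 stops the stated duty to collect pregnancies at 30 days once another anticancer therapy starts, which contradicts the 3-month AESI rule and is shorter than the 120-day window for Cohort A women

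*Protocol*

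**What the plan says.** Master protocol section 8.3.5 covers pregnancies in female participants and in female partners of male participants. Collection runs to 120 days after study treatment ends, or a substudy window, "or 30 days following cessation of study treatment if the participant initiates another anticancer therapy". Substudy 01 section 8.3.5 and Substudy 03 section 8.3 both refer back to the master text, so the clause applies in both cohorts.

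Other sections set different windows, none with a new-therapy stop:

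- Section 8.3.8 lists as an AESI "Pregnancy of a female participant entered in a study as well as pregnancy occurring in a female partner of a male participant", and requires follow-up to outcome.
- Section 8.3.1 says "All SAEs and AESIs will be collected throughout the study period, from the signing of the informed consent form (ICF"), and ends that collection 3 months after the last administration.
- Inclusion criterion I 04 asks women of childbearing potential to use contraception "for at least 120 days (or refer to the individual substudy protocol"). Substudy 01 does not change this. Substudy 03 section 5.1 shortens it to 7 days for Cohort C1. Male participants have 3 days after SAR444245.
- Section 8.2.5 schedules tests at end of treatment and then every 30 (±7) "days until 120 days (or refer to the individual substudy protocol) after the last dose of study treatment".

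**The concern.** A site following 8.3.5 could stop asking about pregnancy at day 30 in a participant who has switched therapy. A site following 8.3.1 and 8.3.8 would go on to 3 months. No text says which prevails.

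For Cohort A women there is a second mismatch. They are asked to use contraception and be tested to day 120, but the section that governs pregnancy collection may have closed by then. Starting another drug does not shorten the elimination time on which I 04 bases its window.

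The written window matters most for participants who stop without progression and then switch. Section 4.1 follows them in clinic "until PD, start of another anticancer therapy, final cohort cut-off, whichever comes first, before moving to the Survival Phone Call Follow-Up Period", and those calls are described as assessing survival status. Section 2.3.1.2.1 states that no pregnancy exposure or outcome data exist for SAR444245, so each case carries information the programme lacks.

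**Working it through.** The plan gives no figure to reproduce. The check compares the windows.

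**Inputs.** Days are counted from the last dose, and cessation of treatment is taken as the same day. Three months is taken as 91 days (assumption; using 90 days lowers the AESI figures by one).

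| Rule | Applies to | Ends | Stops for new therapy? |
|---|---|---|---|
| 8.3.5, no switch | Women and partners | Day 120 or substudy window | – |
| 8.3.5, after switch | Women and partners | Day 30 | Yes |
| 8.3.1 with 8.3.8 | Women and partners, both cohorts | About day 91 | No |
| I 04 and 8.2.5 | Cohort A women of childbearing potential | Day 120 | No |
| Substudy 03, 5.1 (contraception) | Cohort C1 women | Day 7 | No |
| I 04 (contraception) | Male participants | Day 3 | No |

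**Gaps.** Let *s* be the day new therapy starts. Until then the 120-day rule applies. If *s* is after day 30, the clause is read as ending collection on day *s*.

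- Against the AESI rule: 91 − max(30, *s*), not below zero.
- Against the Cohort A window: 120 − max(30, *s*), not below zero.

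| *s* | AESI gap (days) | Cohort A women, gap to day 120 (days) |
|---|---|---|
| 30 or earlier | 91 − 30 = 61 | 120 − 30 = 90 |
| 60 | 91 − 60 = 31 | 120 − 60 = 60 |
| 90 | 91 − 90 = 1 | 120 − 90 = 30 |
| 91 | 0 | 120 − 91 = 29 |
| 120 or later | 0 | 0 |

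At the 90-day maximum, 61 days (31 to 91) are still inside the AESI window. The other 29 (days 92 to 120) are not.

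**Tests.** With end of treatment at day 30, the section 8.2.5 tests fall at about days 30, 60, 90 and 120, so three of the four come after day 30. This is one scenario: the end-of-treatment visit may be held earlier, before new therapy starts, and the ±7-day window can put the day-90 test on either side of day 91.

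**Expected events, as an illustration.** Suppose all 25 Cohort A participants were women of childbearing potential who switched by day 30, with contraceptive failure at 1% per year:

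- 90 days: 25 × 0.01 × 90/365 = 0.062
- Days 31 to 91: 25 × 0.01 × 61/365 = 0.042
- Days 92 to 120: 25 × 0.01 × 29/365 = 0.020

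The population assumption overstates the number. The failure rate may understate it, because section 10.4.2 gives below 1% for consistent and correct use and notes that typical use differs. Cohort C1 women and partners are not counted.

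**The case against.** The strongest reply is that most of the interval is covered elsewhere, by texts that new therapy does not limit. The AESI rule reaches 3 months. The section 8.2.5 tests run to day 120, and a positive test is a pregnancy the site knows about. Section 8.3.5 itself continues: "If a pregnancy is reported, the Investigator will record pregnancy information on the appropriate form and submit it to the Sponsor within 24 hours". Section 10.4.2 adds "The Investigator will collect pregnancy information on any female participant who becomes pregnant while participating in this study", and a parallel duty to try to collect partner pregnancies while the male participant is in the study. A participant in survival follow-up is normally still in the study at day 120. Those who stop with progression also attend Follow-up Visit 1 at 3 months ± 7 days, where the schedule of activities, as extracted, shows a pregnancy test.

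All of this stands. A reader might infer that the clause forbids collection, or that pregnancies after day 30 would be lost. The documents do not support that: the clause ends a stated duty in one section and leaves the others in force.

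A reader might also infer that fetal exposure is a concern beyond day 30 for everyone. The contraception periods point to Cohort A women only. The protocol allows 7 days when SAR444245 is given alone, so the rest of the 120 days probably reflects pembrolizumab; that is an inference.

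The clause may be deliberate, since Amendment 01 edited 8.3.5 and left it in. It may equally be a leftover, since the same amendment removed the equivalent stop for adverse events from 8.3.1. Neither can be shown, and neither removes the contradiction in the current text.

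**Conclusion.** The contradiction is real and lies in current text. In both cohorts, partner pregnancies included, the 8.3.5 cut-off can fall up to about 61 days before the AESI rule ends. That maximum needs a switch by day 30, and the gap is zero from day 91. For Cohort A women of childbearing potential the cut-off can also fall up to 90 days before the contraception and testing window ends, with 61 of those days still under the AESI rule. Days 92 to 120 rest on the scheduled tests, the duty to record a reported pregnancy, and Appendix 4.

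For Cohort C1 women and partners of male participants, the issue is only the conflict with the AESI rule.

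Few events are expected. The 0.06 might be read as an upper bound; it is not, because it uses a perfect-use failure rate and counts Cohort A women only. No efficacy result or dose decision is affected. This is a minor safety-collection correction, worth making because the instructions conflict on an event reportable within 24 hours.

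**What to change.** In section 8.3.5, delete "or 30 days following cessation of study treatment if the participant initiates another anticancer therapy". State that, whether or not new therapy starts, pregnancies are collected:

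- to 120 days in Cohort A women of childbearing potential;
- for at least the 3-month AESI window in Cohort C1 women and in partners of male participants.

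Add a sentence to section 8.3.1 pointing to 8.3.5 for the pregnancy window.

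The cost is one clause deleted and two short statements added. No test is added beyond those section 8.2.5 already requires. Collection runs slightly longer in participants who switch therapy. For those with no later clinic visit, it may mean one question at an existing survival call. The 3-month minimum for partners matches what the AESI rule already asks, so it brings no new exposure-based requirement for them.
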